AE: adverse event; CT: computed tomography; C: cycle; D: day; C1D1: cycle 1 day 1; ECG: electrocardiogram; ECHO: echocardiogram; ECOG: Eastern Cooperative Oncology Group; ELISpot: enzyme-linked immunospot; EoT: end-of-treatment; HLA: human leukocyte antigen; ICF: informed consent form; INR: international normalization ratio; IRT: interactive response technology; MUGA: multigated acquisition scan; Obs: observation; PGx: pharmacogenomics; PT: prothrombin time; SAE: serious adverse event; WOCBP: women of childbearing potential; WT1: Wilms' tumor 1 protein.

a. Obtained predose.

b. Obtained predose and postdose (including flushing) (vital signs: hourly [± 10 minute window] for up to 4 hours postdose; ECG: 1 to 2 hours postdose) on C1D1 and C2D1.

c. Height measurement performed only at screening. Weight measurement should be performed at screening and day 1 of each cycle.

Footnotes continued on next page

- d. Includes medications taken within 28 days prior to C1D1.
- e. WOCBP must have a negative serum or urine pregnancy test (minimum sensitivity 25 IU/L or equivalent units of human chorionic gonadotropin) within 72 hours prior to the start of study treatment.
- f. The 12-lead ECGs will be recorded in triplicate (at least 2 minutes apart per time point) and transmitted electronically for central reading.
- g. Laboratory samples will be analyzed by the institution's local laboratory. However, sample results must also be submitted for centralized data entry. Laboratory tests and/or ECG can be repeated during screening period.
- h. Laboratory samples will be analyzed by the institution's local laboratory and results will be submitted for centralized data entry.
- i. Chest X-ray (or CT of chest) does not need to be repeated if performed within 2 weeks prior to start of screening.
- j. MUGA scans or ECHO (per standard of care) performed at screening or within 28 days prior to screening will be accepted.
- k. Screening samples may be collected up to 28 days prior to C1D1. End of treatment bone marrow sample does not need to be repeated if collected within 2 weeks of the last disease assessment. Samples must be submitted to a central laboratory for analysis. If bone marrow aspirate is unobtainable (e.g., dry tap), an additional ethylenediaminetetraacetic acid tube of whole blood should be collected instead. Bone marrow aspirate is required, and bone marrow biopsy is preferred. In case of inadequate aspirate, bone marrow biopsy is required.

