- c. After the completion of Observation Period 1 (12 weeks), subjects remaining in the study will have bone marrow samples collected in Observation Period 2 every 3 months or if there is suspicion of relapse in the whole blood. Samples must be submitted to a central laboratory for analysis. If bone marrow aspirate is unobtainable (e.g., dry tap), an additional ethylenediaminetetraacetic acid tube of whole blood should be collected instead. Bone marrow aspirate is required, and bone marrow biopsy is preferred. In case of inadequate aspirate, bone marrow biopsy is required.
- d. Samples must be submitted to a central laboratory for analysis.
- e. Maximum of 1 sample collected during Observation Period 2.
- f. Maximum of 5 samples collected during Observation Period 2.
- g. Laboratory samples will be analyzed by the institution's local laboratory and results will be submitted for centralized data entry. Subjects who are transfusion dependent should be subjected to more frequent laboratory assessments to determine transfusion need based on the judgment of the investigator.
- h. Subjects not proceeding to observation period 2 are required to provide a bone marrow sample at the last visit of observation period 1.
- i. Concomitant medications and AEs are collected until post-treatment period and at least 30 days after last IP dose and prior to the start of new anticancer treatment. In addition, the following will be collected regardless of the start of new anticancer therapy: Any IP-related SAE that is ongoing will be followed until resolved, and any SAE that is deemed to be related to IP by the investigator.
- j. Applicable only for subjects in dose expansion phase.

Table 4 Schedule of Replication Competent Lentivirus for Dose Escalation and Dose Expansion

Assessment	C1D1	3 Months After Treatment Initiation or End of Treatment, Whichever is First	6 Months After Treatment Initiation	12 Months After Treatment Initiation	18 Months After Treatment Initiation ^c
Window	0	± 1 day	± 1 month	± 1 month	± 1 month
Blood Sample for RCL ^a	X ^b	X	X	X	X

C1D1: cycle 1 day 1; RCL: replication competent lentivirus

a. If there are positive results, additional follow-up assessments may be required. Refer to Section [7.6.4](#) Sample for Replication Competent Lentivirus.

b. Obtained predose.

c. Only applicable to subjects in the expansion cohort.

Table 5 Pharmacokinetics Sample Collection Schedule-Dose Escalation Cohort and Dose Expansion Cohort

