3 STUDY OBJECTIVE(S) AND ENDPOINT(S)

The study objectives and endpoints for this study are provided in [Table 7](#).

Table 7 Study Objectives and Endpoints

Objective(s)	Endpoint(s)
Primary	
• To evaluate the safety and tolerability of ASP7517• To determine the RP2D and/or the MTD of ASP7517 (phase 1)• To evaluate the clinical response of ASP7517 
• Safety and tolerability as noted by: DLTs, AEs, SAEs, laboratory test results (serum, chemistry, hematology, coagulation, and urinalysis, pregnancy test) ECGs, vital signs, physical exams and ECOG performance status scores• CRc rate for subjects with R/R AML and (CR + BM CR + PR) rate for R/R higher risk MDS (phase 2)
Secondary	
• To evaluate other measures of anticancer activity of ASP7517 
• Duration of remission• EFS• OS• CR, best response (CRc + PR) and CRh rates for subjects with R/R AML• CR, HI and objective response (CR + BM CR + PR + HI) rates for subjects with R/R higher risk MDS
Exploratory	
• To evaluate potential genomic, proteomic and/or other biomarkers that may correlate with treatment outcome• To evaluate pharmacodynamic activities of ASP7517• To evaluate pharmacokinetics of ASP7517, which is determined by the kinetics of the cells 
• Exploratory biomarkers that may correlate with treatment outcome of ASP7517• Pharmacodynamic effects of ASP7517, such as changes in:
○ Cytokine expression and secretion (e.g., IFNg)○ WT1-specific T lymphocytes (e.g., cytotoxic T lymphocytes)○ Immune cell populations (NKT cells, NK cells, etc.)• Cellular DNA load and kinetic parameter estimates for ASP7517

AE: adverse event; AML: acute myeloid leukemia; BM: bone marrow; CR: complete remission; CRc: composite complete remission; CRh: complete remission with partial hematologic recovery; DLT: dose limiting toxicity; ECG: electrocardiogram; ECOG: Eastern Cooperative Oncology Group; EFS: event-free survival; IFNg: interferon gamma; HI: hematologic improvement; MDS: myelodysplastic syndrome; MTD: maximum tolerated dose; NK: natural killer; NKT: natural killer T; OS: overall survival; PR: partial remission; R/R: relapsed/refractory; RP2D: recommended phase 2 dose; SAE: serious adverse event; WT1: Wilms' tumor 1 protein.

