    - Bone marrow blasts decreased by  $\geq 50\%$  over pretreatment but still  $> 5\%$
    - Cellularity and morphology not relevant
  - Marrow CR: For subjects to be classified as being in marrow CR at a post-baseline visit, they must have all of the following for a minimum of 4 weeks:
    - Bone marrow:  $\leq 5\%$  myeloblasts and decrease by  $\geq 50\%$  over pretreatment
      - Peripheral blood: if HI responses, they will be noted in addition to marrow CR
  - Hematologic Improvement (HI): For subjects to be classified as having hematologic improvement (HI) at a post-baseline visit, they must have 1 measurement of the following, maintained for at least 8 weeks without ongoing cytotoxic therapy:
    - HI – erythroid:

- Hemoglobin increase of  $\geq 1.5$  g/dL or
- For RBC transfusions performed for hemoglobin  $\leq 9.0$  g/dL: reduction in RBC units transfused in 8 weeks by  $\geq 4$  units compared to the number of units transfused in the 8 weeks prior to treatment
- HI – platelets:
  - For pre-treatment platelet count of  $>20 \times 10^9$  /L platelet, absolute increase of  $\geq 30 \times 10^9$  /L
  - For pre-treatment platelet count of  $< 20 \times 10^9$  /L, platelet absolute increase of  $> 20 \times 10^9$  /L and  $\geq 100\%$  increase from pre-treatment level
- HI – neutrophils:
  - Neutrophil count increase of  $\geq 100\%$  from pre-treatment level and an absolute increase of  $> 0.5 \times 10^9$  /L
- Relapse after CR or PR: For subjects to be classified as relapsing after CR or PR requires at least one of:
  - Return to pre-treatment bone marrow blast percentage
  - Decrement of  $\geq 50\%$  from maximum response levels in granulocytes or platelets
  - Transfusion dependence or hemoglobin level  $\geq 1.5$  g/dL lower than prior to therapy
- Stable Disease (SD): For subjects to be classified as having Stable Disease (SD), they must fail to achieve at least PR but show no evidence of progression for  $>8$  weeks
- Progressive Disease (PD): For subjects to be classified as having Progressive Disease (PD), they must show blast level increases depending on prior levels as follows:
  - For patients with:
    - $<5\%$  blasts:  $\geq 50\%$  increase in blasts to  $> 5\%$  blasts
    - $5\%-10\%$  blasts:  $\geq 50\%$  increase to  $> 10\%$  blasts
    - $10\%-20\%$  blasts:  $\geq 50\%$  increase to  $> 20\%$  blasts
    - $20\%-30\%$  blasts:  $\geq 50\%$  increase to  $> 30\%$  blasts
  - Or any of the following:

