### 6.2.5 Previous and Concomitant Transfusions

All transfusions received by subjects within 28 days prior to Day 1 of Cycle 1 through end of treatment will be recorded on the eCRF. Data will include the date, blood product, start and stop date, indication, and the number of units given.

Frequency tabulations of subjects received transfusions and blood product will be presented for previous transfusion and concomitant transfusion by cohort and dose level for SAF.

Descriptive statistics will be presented for number of transfusion unit received per subject.

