## 6.4 Analysis of Efficacy

Efficacy analyses will be conducted on the FAS and RAS. The interpretation of results from statistical tests will be based on the FAS. The RAS will be used to assess the robustness of the results from the statistical tests based on the FAS. All randomized subjects will be analyzed according to the treatment to which they are randomized/assigned. Efficacy data from the China cohort will be analyzed separately.

Derived response based on central assessment supplemented by local assessment: response will be derived based on the definitions in Section 7.1.1 using centrally evaluated myeloblast counts from bone marrow aspirate or biopsy assessments whichever is present (if both are present, both must qualify for the criteria) and centrally evaluated hematology results including ANC, platelet count and blast count in peripheral blood. If neither central bone marrow aspirate nor biopsy is available at baseline assessment, then myeloblast counts from locally evaluated bone marrow aspirate/biopsy assessments (if both are present, both must qualify for the criteria) will be used for all timepoints of assessment. Missing hematology results will not be imputed.

Derived response will be considered as primary and investigator reported response will be considered as supportive.

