### 6.4.2.2 Objective Response Rate (ORR)

Objective Response Rate (ORR) is defined for MDS subjects as the number of subjects who achieve CR, BM CR, PR or HI at any of the postbaseline visits divided by the number of subjects in the analysis population. ORR is applicable for MDS subjects only.

The ORR will be estimated and its 90% confidence interval (CI) will be constructed by Clopper-Pearson method by dose level using the RAS.

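### SAP 6.2.5 records 28 of the 56 pre-treatment days and no pre-transfusion hemoglobin, so erythroid HI by transfusion reduction, a component of MDS ORR, cannot be evaluated as written

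*SAP*

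**What the plan says.** SAP 6.2.5 sets the transfusion record: "All transfusions received by subjects within 28 days prior to Day 1 of Cycle 1 through end of treatment will be recorded". The items it lists are dates, blood product, indication and number of units. Pre-transfusion hemoglobin is not among them.

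The HI definition in SAP 5.1.1, with the same wording in protocol 7.1.1.2, has two erythroid routes: a hemoglobin rise, or a reduction in RBC transfusion. The second route counts transfusions given for hemoglobin of 9.0 g/dL or less. It requires at least 4 fewer units over 8 weeks, "compared to the number of units transfused in the 8 weeks prior to treatment". HI must also be maintained for at least 8 weeks without ongoing cytotoxic therapy.

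HI alone makes an MDS subject a responder. SAP 6.4.2.2 bases ORR on "the number of subjects who achieve CR, BM CR, PR or HI at any of the postbaseline visits", divided by all subjects in the analysis population, and adds: "The ORR will be estimated and its 90% confidence interval (CI) will be constructed by Clopper-Pearson method by dose level using the RAS". SAP 6.4 says: "Derived response will be considered as primary and investigator reported response will be considered as supportive". Protocol Table 7 lists as secondary endpoints "CR, HI and objective response (CR + BM CR + PR + HI) rates for subjects with R/R higher risk MDS". The SAP has no section for a separate HI rate, so in the SAP the issue reaches results through ORR.

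**The concern.** The criterion needs 56 days of pre-treatment transfusion history and the record covers the last 28. No other look-back fills the gap. The prior-medication footnote in protocol Tables 1 and 2 reads "Includes medications taken within 28 days prior to C1D1", and the baseline transfusion-status period in SAP 5.1.11 also starts 28 days before first dose. Protocol Tables 1 to 3 have no transfusion row. No rule says how to apply an 8-week criterion to a 4-week count, and protocol 9.8 sets a general principle of no imputation, with exceptions only for dates.

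At stake is one component of MDS ORR, a rate that is still estimated with an interval when PFS, EFS, OS and duration of response have been reduced to listings. A subject whose only response is by this route may be counted as a non-responder because of what was recorded, not because of what happened.

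**Working it through.** The documents state no expected HI rate or ORR, so there is no planned figure to reproduce.

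**1. Windows.** Needed: 8 × 7 = 56 days. Recorded: 28 days. Share recorded: 28/56 = 50%.

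**2. Direction.** Let B be units in the recorded 28 days, U units in the unrecorded 28 days before them, and T units in an on-study 8-week window. Assume for now that every unit qualifies and that T is fully recorded. The criterion is B + U − T ≥ 4. The test on recorded data is B − T ≥ 4. Because U ≥ 0, passing the recorded test implies meeting the criterion, while failing it leaves the matter open. Enumerating B and U from 0 to 19 and T from 0 to 29 gives 0 false positives and 3,655 false negatives. Example: 8 units in 8 weeks (4 in the last 28 days) falling to 2 is a true fall of 6, but the recorded fall is 4 − 2 = 2 and the response is missed. A fall from 8 to 0 is still confirmed, since 4 − 0 = 4.

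**3. Size with one on-study window.** Transfusion rates are not in the documents, so I assume independent Poisson counts with r units per week before treatment and s on study. The 8-week baseline has mean 8r, the recorded baseline 4r and the on-study count 8s. The probability of a fall of at least 4 is Σ P(baseline = b) × P(T ≤ b − 4). For r = 1 and s = 0 this is P(Poisson(8) ≥ 4) = 0.958 against P(Poisson(4) ≥ 4) = 0.567, a ratio of 0.592.

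| Units per week, before → on study | 56-day baseline | 28-day baseline | Share confirmed |
|---|---|---|---|
| 1 → 0 | 0.958 | 0.567 | 59% |
| 2 → 0 | 1.000 | 0.958 | 96% |
| 1 → 0.25 | 0.784 | 0.261 | 33% |
| 2 → 0.5 | 0.976 | 0.552 | 57% |

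If units are given in pairs (a fall of at least 2 two-unit episodes), the first row becomes 0.908 against 0.594 (65%) and the last 0.930 against 0.574 (62%).

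**4. Size with longer treatment.** ORR counts HI at any post-baseline visit, so the 8-week window can roll. The last planned visit of cycle 6 is day 5 × 28 + 15 = 155, and EoT may fall up to 7 days later, on day 162. Taking the best 56-day window up to then, by simulation, the confirmed share rises from 33% to about 51% (1 → 0.25) and from 57% to about 83% (2 → 0.5). The rows where need stops completely do not change.

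**5. Effect on ORR.** Loss = f × (1 − share confirmed), where f is the share of MDS subjects who respond only by this route. The documents do not give f. With one window and f = 10%, the four rows lose 4.1, 0.4, 6.7 and 4.3 points. Across the four rows the range is 0.2 to 3.3 points for f = 5%, 0.4 to 6.7 for 10% and 0.8 to 13.3 for 20%.

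**6. Relaxing the qualifying assumption.** Only transfusions given for hemoglobin of 9.0 g/dL or less count. If 10%, 25% or 50% of units (assumed) were given above that level, then at 1 unit per week falling to none, 0.6%, 4% or 29% of confirmations on raw units would be false.

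**7. Doubling the 28-day count.** This errs both ways. With 1 unit per week and no real change, it calls 0.230 responders against 0.189 on the full 8-week baseline.

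**The case against.** The strongest reply has four parts.

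First, SAP 6.2.5 sits under Study Population and governs descriptive tables. The eCRF is not in the documents, and protocol 7.3.5 refers certain transfusion procedures to eCRF guidelines that we cannot see. The 56-day history may already be collected. This stands as a limit: a reader might infer that the data are lost, and the documents do not show that. They show only that the stated record does not cover the stated criterion, and the text needs correcting in either case.

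Second, a reader might infer that a recorded fall of 4 units proves response. It does not. The hemoglobin condition is part of the criterion and is not recorded, and step 6 shows that false confirmations are possible. HI must also last 8 weeks without cytotoxic therapy. This objection stands in full and shapes the fix.

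Third, a reader might infer that ORR is simply biased downward. No passage says that the raw 28-day count will be subtracted. SAP 6.4 lists the inputs to derived response as myeloblasts, ANC, platelets and peripheral blasts, and names neither transfusions nor hemoglobin. If on-study days without a record were read as transfusion-free, that error would push upward. Protocol Table 3 says "Concomitant medications and AEs are collected until post-treatment period and at least 30 days after last IP dose", so later records may exist, but SAP 6.2.5 stops at end of treatment. The downward direction is therefore conditional.

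Fourth, every magnitude rests on assumed rates. This stands, and the range runs from negligible to material.

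**Conclusion.** The mismatch is real and on the page. Half of the comparator window and the pre-transfusion hemoglobin are not among the recorded items, and no rule bridges the gap, so erythroid HI by transfusion reduction cannot be evaluated as written.

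The error can only miss responders, and so lower MDS ORR, if three conditions hold: the 28-day count is used unscaled, the on-study 8-week window is fully recorded, and all counted units qualify. Under those conditions and assumed Poisson use, 33% to 96% of true responders by this route are confirmed with a single window, and more when treatment is long. The effect on ORR cannot be sized from the documents, because the share of subjects who respond only by this route is not given.

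The reach is limited. ORR is a descriptive secondary rate. The AML and MDS primary endpoints, the BOP2 decisions and the hemoglobin, platelet and neutrophil HI routes are unaffected. The point merits a correction to the SAP and the data collection, and it does not call the trial's main conclusions into question.

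**What to change.** In SAP 6.2.5 and the eCRF instructions, record RBC transfusions with date, units and pre-transfusion hemoglobin from 56 days before cycle 1 day 1, by chart look-back for subjects already enrolled. If the eCRF already captures this, correct 6.2.5 to say so.

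Where the earlier 28 days cannot be retrieved, add this rule to the SAP:

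- Accept response by this route only if qualifying units (hemoglobin of 9.0 g/dL or less) in the recorded 28 days exceed all units in a fully recorded on-study 8-week window by at least 4, and the other HI conditions are met (maintained for 8 weeks, no ongoing cytotoxic therapy). Qualifying units before treatment can only be undercounted, and on-study units only overcounted, so the rule is conservative.
- Otherwise classify the subject as not evaluable by this route, let the other HI routes count, keep the subject in the ORR denominator and report the number affected.
- Never count unrecorded days as transfusion-free.
- Doubling the 28-day count, if shown at all, should be a labelled sensitivity analysis.

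The cost is SAP and eCRF text plus retrospective retrieval. SAP 3.0 is dated June 2023 and the study began in about 3Q2019, so some histories will not be recoverable and some subjects will stay not evaluable by this route. No extra visit or procedure is needed.

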### 6.2.6 Prior Chemotherapy for Primary Disease

Frequency tabulations of subjects with prior AML/MDS chemotherapy, regimen, type of treatment, best response to prior AML/MDS therapy, lines of therapy received and subjects with prior Tyrosine Kinase Inhibitor (TKI) therapy will be presented by cohort and dose level for SAF. Descriptive statistics will be presented for duration of response to prior AML/MDS therapy.

### 6.2.7 Non-Medication Therapy

Frequency tabulations of subjects with non-medication therapy and reason for use will be presented by cohort and dose level for SAF. Number of non-medication therapy received per subject will be summarized using descriptive statistics.

## 6.3 Study Drug

### 6.3.1 Exposure

The following information on drug exposure will be presented with descriptive statistics (n, mean, standard deviation, median, minimum, maximum) for the SAF:

- Duration of exposure (days)
  - Duration of exposure to a study drug will be calculated in days, using the following formula:
$$\text{Duration of exposure} = (\text{Last date of exposure} - \text{date of first dose}) + 1$$
where last date of exposure = initial infusion date of the last cycle + 27, death date if death occurs within last cycle, start date of new anticancer therapy, or treatment discontinuation date.
    - When the start or stop date is missing, then the exposure will be treated as missing.
  - (Last date of exposure – date of first dose) + 1; where last date of exposure = initial infusion date of the last cycle + 27, death date if death occurs within last cycle, start date of new anticancer therapy, or treatment discontinuation date.
- Cumulative actual dose (# of cells)
  - Total amount of IP administered to the patient from first dose date to last dose date
- Number of cycles initiated
  - Total number of cycles with non-zero dosing in the cycle
- Actual dose intensity
  - Defined as the cumulative actual dose divided by number of cycles
- Relative dose intensity (RDI; %)
  - Actual Dose Intensity
  - $\times 100$
  - Planned Dose Intensity

Number and percentage of subjects with infusions not administered, delays, interruptions, or premature discontinuations at any cycle will be presented for the SAF. The reasons for infusions not administered, delays, interruptions, and premature discontinuations at any cycle will be listed.

